### *Randomization during the nested cluster-randomized trial*

Each attending anesthesiologist and in-room provider will be randomized to either of the two interventions that is aimed at their user group. The randomization will occur at the start of the nested cluster-randomized trial period or at the time she/he enters the study within that period. Randomization at the provider level rather than at the patient level aims to prevent contamination and therefore dilution of the implementation effect. Randomization of the attending anesthesiologists will be stratified for the particular anesthesia expertise groups, e.g. vascular surgery anesthesia and neuroanesthesia. In-room providers will also be randomized per participating center, but stratified for being a resident, a CRNA or a SRNA. Randomization of CRNAs will be stratified on the OR-locations within their center where they mostly work. Stratified randomization will be performed using a block size of four.

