## Sample size calculation

Sample size calculations were performed in *R* software. As mentioned earlier, we calculated

sample sizes for each of the participating centers, because they will use a different primary end point. The required sample sizes were calculated for both primary end points. Sample size calculations assumed a power of 0.8 and a Type 1 error rate (alpha) of 0.05. Based on earlier experiences with decision support intervention studies, we assumed there would be no clustering of primary end point data at the provider level.

Using historic data from the VUMC, the incidence of any MAP below 65 mmHg were estimated at 60% for patients that meet the inclusion criteria. Within this study population – any MAP < 65 mmHg – the incidence of AKI stage I was 9.8%. We derived the assumed treatment effect from the odds ratio (OR) reported by Sun et al. They reported an odds ratio of 1.8 (originally 1.84) for postoperative AKI in patients that had a MAP below 60 mmHg for 10 minutes or more. Thus the possible treatment effect within patients having a MAP < 60 mmHg for 10 minutes or more is then an OR of 0.56 (the inverse of 1.8). Within the study population (any MAP < 65 mmHg), the incidence of MAP < 60 mmHg for 10 minutes was 43%. Applying the OR 0.56 to an incidence of 43% resulted in an overall OR of 0.78 within the study population. The intervention phase (9 months) is four times shorter than the preintervention phase (36 months), resulting in a fraction of 0.20 of the total study period (9 divided by 45). As the intervention might not be as efficient during the nested cluster-randomized trial period, we used only half of the three months trial period, reducing the fraction of the intervention phase to 0.17. Additionally, we included a 20% margin of error to the sample size of the intervention period. The resulting calculated sample size is 2,005 procedures for the intervention phase and 8,019 procedures for the preintervention phase (Table 3). With an average of 275 procedures per month meeting the inclusion criteria, the calculated sample size is feasible within the specified time periods.

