## Statistical analysis

### *Primary end points*

The analysis of the primary end point will be performed under the intention-to-treat principle, and only include patients that have had a MAP below 65 mmHg for at least one minute during the procedure. As the study is an interrupted time series design, segmented regression models will be used for both primary end points. The different study groups within the nested cluster-randomized trial will not be separately analyzed because of a too small sample size.

A two-sided alpha of 0.05 will be considered to be statistically significant. Continuous variables will be visually assessed for a normal distribution using histograms and QQ-plots. In descriptive statistics, parametric variables will be expressed as means with standard deviations, nonparametric variables will be expressed as medians with interquartile ranges, and discrete variables will be expressed as numbers with percentages. Missing data will be multiply imputed

using a regression approach. Before multivariable modelling, all continuous variables will be tested for nonlinearity using restricted cubic splines.

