#### *Secondary end points: process level*

In contrast to the primary end point and other secondary patient outcome, clustering at the attending level is expected for process level end points. Quantitative analysis on process level end points will thus account for clustering using segmented regression models that also included random effects. For these mixed effects models we will exclude attending anesthesiologists with a low case volume of eligible procedures from the analysis.

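### AKI and the secondary patient outcomes are analysed with no allowance for provider clustering; the likely understatement of the standard errors is modest, and attending-clustered errors would remove most of it cheaply

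*Combined protocol and SAP*

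**What the plan says.** Under Sample size calculation the plan says that "we assumed there would be no clustering of primary end point data at the provider level". The reason given is "Based on earlier experiences with decision support intervention studies", with one citation. The title in the reference list shows a study of risk assessments, antiemetic prescription and postoperative nausea and vomiting. No ICC is quoted and no AKI data are offered.

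Under Statistical analysis, Primary end points, AKI is analysed by segmented regression, with no provider effect and no cluster-robust variance mentioned. The secondary patient outcomes follow the same approach. The section on process-level end points takes the other course: "In contrast to the primary end point and other secondary patient outcome, clustering at the attending level is expected for process level end points". Random effects are specified there only. The incidence, depth and duration of intraoperative hypotension (IOH) are listed as process-level end points.

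The decision support is delivered to providers and, in the nested trial, allocated by provider. Attendings work in specialty groups: "Randomization of the attending anesthesiologists will be stratified for the particular anesthesia expertise groups". Table 3 varies the share of hypotension treated and the odds ratio for short IOH. It has no row for clustering.

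**The concern.** The intervention works by changing what providers do, and the plan's hypothesis is that less IOH means less AKI. If attendings differ in AKI risk, and if the mix of attendings or their response to the alerts changes between the 36-month and 9-month periods, the estimated level change carries variation that a model of independent procedures does not count. The naive standard error is then too small and the nominal 5% two-sided error rate is exceeded. This matters because the comparison is with historic controls, so the confidence interval for the level change carries the conclusion. The same applies to mortality, ICU use and length of stay.

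**Working it through.** **Inputs from the plan.** Preintervention AKI: "the incidence of AKI stage I was 9.8" percent. Effect: the plan's calculation "resulted in an overall OR of 0.78 within the study population". Prolonged IOH (MAP below 60 mmHg for 10 minutes) in 43% of the study population, with an odds ratio of 1.8 for AKI. Planned size: 8,019 preintervention and 2,005 intervention procedures. Power 0.80, two-sided alpha 0.05.

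**Assumptions (not in the documents).** Number of providers K, ICC, the correlation r of a provider's effect between periods, turnover, and the between-attending SDs on the logit scale.

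**1. The plan's own figure.** Table 3 gives 9,690 procedures before the 20% margin. A pooled two-proportion formula with intervention share 7.5/43.5 gives 9,679 when 0.78 is applied as a risk ratio (9.8% to 7.64%), the closest match found. Applied as an odds ratio (9.8% to 7.81%), it gives 11,462. That is a separate matter. Here the point is only that no design effect is needed to reach the stated size, so the ICC was taken as 0.

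**2. Clustering that reaches AKI only through IOH.** Solve 0.57 × p0 + 0.43 × p1 = 0.098 with odds ratio 1.8: p0 = 7.5%, p1 = 12.8%. The squared correlation of prolonged IOH with AKI is 0.43 × 0.57 × (0.128 − 0.0754)² / (0.098 × 0.902) = 0.0077. The AKI ICC by this route is that value times the IOH ICC:

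| Assumed IOH ICC | Implied AKI ICC |
|---|---|
| 0.05 | 0.0004 |
| 0.10 | 0.0008 |
| 0.20 | 0.0015 |

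At 0.0008, with K = 40 and r = 0, the design effect is 1.06 and the standard error rises by a factor of 1.03.

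**3. Clustering from any source, before-after contrast.** For equal-sized providers seen in both periods, the variance relative to the unclustered one is

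DE = (1 − ICC) + [2 × ICC × (1 − r) / K] / (1/2,005 + 1/8,019).

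For K = 80, ICC = 0.01, r = 0.5: 0.99 + (0.000125 / 0.000623) = 1.19. With odds ratio 0.78, power without clustering is 79.3%.

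| K | ICC | r | DE | SE factor | Power | Error of naive test |
|---|---|---|---|---|---|---|
| 80 | 0.01 | 1 | 0.990 | 0.995 | 79.7% | 4.9% |
| 80 | 0.01 | 0.5 | 1.190 | 1.09 | 71.7% | 7.2% |
| 80 | 0.01 | 0 | 1.391 | 1.18 | 64.6% | 9.7% |

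The first row shows that stable provider differences do no harm.

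**4. Simulated segmented model.** Logistic model with linear time and a step at month 36; 45 months × 223 procedures (10,024 / 45 = 223); AKI 9.8%; attending intercept SD 0.4; 40 to 60 attendings; 2,000 runs for the turnover rows. The table gives the true SD of the level change divided by the naive standard error.

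| Scenario | Ratio |
|---|---|
| Same attendings, no variation in response | 0.98-1.01 |
| 40% turnover spread over 45 months, response SD 0.125 | 1.03-1.09 |
| 40% turnover, all at month 36, response SD 0.125 | 1.13-1.18 |

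A two-sided 5% test has true error 2 × [1 − Φ(1.96 / ratio)]. Ratios of 1.03 to 1.09 give 5.7% to 7.2%; 1.13 to 1.18 give 8.3% to 9.7%. A separate segmented simulation (60 providers, ICC 0.01, 1,500 runs) gave smaller ratios for the level change: 0.99 with stable providers, 1.04 at r = 0.5, and 1.05 with 30% of providers replaced.

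**5. Does the remedy work?** Attending-clustered standard errors kept the error rate at 5.0-7.0% in every scenario tried.

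**The case against.** The plan's assumption is declared, and its sections agree with one another: both say that clustering is not expected for the primary end point. A reader might infer an internal contradiction from expecting IOH to cluster while assuming that AKI does not. The documents do not support that: on the plan's own figures (step 2), IOH clustering alone passes almost nothing to AKI. What the cited study reported about clustering cannot be seen, so it cannot be called inadequate; one can say only that its title concerns another outcome.

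A reader might also apply the usual design effect, 1 + (m − 1) × ICC. With K = 80, m = 10,024 / 80 = 125, so ICC 0.01 would give 2.24 against 1.19 in step 3. That formula does not fit a contrast in which the same providers contribute to both periods. Expertise groups, as stable case-mix differences, largely cancel for the same reason.

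A third tempting step is to let attendings' responses to the alerts vary with an SD of 0.4 to 0.6, which yields much larger error rates. The plan's whole effect is ln 0.78 = −0.25. If responses lie between none and full, their SD cannot exceed 0.125. Even if some attendings had prolonged IOH in every patient (odds ratio 0.56, logit −0.58), the limit is 0.29. A mean-zero response with SD 0.4 also shifts the marginal effect by about 0.05, so its rejections are not all false positives.

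Finally, a reader might think low-volume attendings are dropped from the AKI analysis. The plan limits that exclusion to the process-level mixed models.

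These objections stand. They limit the size of the problem but do not remove it, since turnover, changing case mix and uneven response do not cancel and nothing prespecified would detect them.

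**Conclusion.** The point holds as a modest one. Zero clustering of AKI is asserted without AKI data, and neither the primary model nor the secondary patient-outcome models protect against its failure. Under gradual turnover and modest variation in response, the true standard error exceeds the naive one by about 3-9%. An abrupt 40% change of attendings at month 36 raises this to about 13-18%; with stable attendings it is essentially nil. All of this rests on assumed numbers of attendings, SDs and turnover. The documents do not show that the assumption is false or that the primary test is seriously invalid. The change is a cheap improvement, not the repair of a demonstrated error.

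**What to change.** State in the analysis section that the primary AKI model and the secondary patient outcomes will be reported with attending-clustered, small-sample-corrected standard errors, or with a random attending intercept plus a random phase effect. Clustered errors leave the estimate itself unchanged; the mixed logistic model moves it to an attending-specific odds ratio, so the choice should be fixed in advance.

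Estimate the AKI ICC by attending from the 36-month historic cohort and report it beside the sample size, so that the zero-clustering assumption rests on the trial's own outcome. Note that in-room providers are crossed with attendings, so clustering on attending alone does not capture both; say how this will be examined.

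The cost is a few lines of text and no new data collection. Intervals may be slightly wider, and almost unchanged if the assumption is right.

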The calculations above assume that all episodes of prolonged hypotension will be treated during the intervention phase, which is unlikely. However, it also assumes that preventing shorter amounts of IOH (< 10 minutes) does not have any effect on patient outcome (an OR of 1.0), which is also unlikely. Consequently, the second assumption may compensate for the first assumption. As a sensitivity analysis we calculated the sample sizes for different combination of a different treatment percentage and an OR > 1.0 for patients with a MAP < 60 for 1-10 minutes

(Table 3). This sensitivity analysis shows that the calculated sample sizes indeed include an error margin for the assumption on the IOH treatment percentages.

Table 3 - Sample size calculation with sensitivity analyses

	Sample sizes calculated			
	Center	n	intervention phase	preintervention phase
sample size including 20% error margin	AKI (VUMC)	10024	2005	8019
sample size without 20% error margin	AKI (VUMC)	9690	1671	8019
80% of hypotension treated OR 1.1 MAP < 60 for 1-10 min.	AKI (VUMC)	11432	1971	9461
70% of hypotension treated OR 1.2 MAP < 60 for 1-10 min.	AKI (VUMC)	11910	2054	9857

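### Table 3 matches 0.78 used as a risk ratio although the text calls it an odds ratio, and its sensitivity rows show a shortfall where the text claims an error margin

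*Combined protocol and SAP*

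**What the plan says.** The Sample size calculation takes an AKI stage I incidence of 9.8% among patients with any MAP below 65 mmHg. It assumes an odds ratio of 0.56 (the inverse of 1.8) in the 43% who have MAP below 60 mmHg for 10 minutes, and then writes: "Applying the OR 0.56 to an incidence of 43% resulted in an overall OR of 0.78 within the study population". On error rates: "Sample size calculations assumed a power of 0.8 and a Type 1 error rate (alpha) of 0.05". The Statistical analysis section adds: "A two-sided alpha of 0.05 will be considered to be statistically significant". Half of the three-month nested trial is discounted, so the intervention fraction is 0.17. The margin is described as follows: "Additionally, we included a 20% margin of error to the sample size of the intervention period".

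Table 3 gives 9,690 without the margin (1,671 intervention, 8,019 preintervention) and 10,024 with it (2,005 and 8,019). Two sensitivity rows follow. With 80% of hypotension treated and an OR of 1.1 for 1-10 minutes, the need is 11,432 (1,971 and 9,461). With 70% treated and an OR of 1.2, it is 11,910 (2,054 and 9,857).

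The text concedes that treating every prolonged episode is unlikely, but adds that "it also assumes that preventing shorter amounts of IOH (< 10 minutes) does not have any effect on patient outcome", which it also calls unlikely. It concludes: "This sensitivity analysis shows that the calculated sample sizes indeed include an error margin for the assumption on the IOH treatment percentages".

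**The concern.** Two statements do not follow from the plan's own inputs.

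First, an odds ratio and a risk ratio of 0.78 are different targets at a 9.8% base rate: 7.81% and 7.64% AKI. The gap looks small, but sample size varies with the inverse square of the difference from 9.8%, so it moves the total by almost a fifth.

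Second, the sensitivity rows ask for more procedures than are planned, yet the text reads them as evidence of a reserve. The rows also never vary the treated percentage alone, because each pairs less treatment with added benefit from short hypotension. The share of patients with 1-10 minutes below 60 mmHg is not given, so the rows cannot be recomputed from the document.

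At stake is whether a reader can tell what effect the study is powered for and how robust that power is. Feasibility is not at stake.

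**Working it through.** **Inputs.** From the Sample size calculation: p_A = 0.098, power 0.80, alpha 0.05, 43% exposed, OR 1.8. From Statistical analysis: two-sided testing. Allocation is k = 7.5/36 = 0.2083 (7.5/43.5 = 0.17). No clustering, as the plan assumes.

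**Formula** (pooled two-proportion, no continuity correction), with p̄ = (p_A + k·p_B)/(1 + k):

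n_pre = [1.960·√(p̄(1−p̄)(1+1/k)) + 0.842·√(p_A(1−p_A) + p_B(1−p_B)/k)]² / (p_A − p_B)², and n_int = k·n_pre.

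**Step 1: reproduce Table 3.**
- As a risk ratio: p_B = 0.098 × 0.78 = 0.0764. n_pre = (1.3794 + 0.5501)²/0.02156² = 8,009 and n_int = 1,669, total 9,678. Table 3 has 8,019 + 1,671 = 9,690, a 0.1% difference. Adding the margin, 1,671 × 1.2 = 2,005.
- As the stated odds ratio: odds 0.098/0.902 × 0.78 = 0.0847, so p_B = 0.0781. n_pre = (1.3813 + 0.5545)²/0.01988² = 9,486 and n_int = 1,976, total 11,462, which is 18% above 9,690.

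Other formulas at OR 0.78 give totals of 10,422 (unpooled), 11,149 (arcsine), 11,813 (continuity-corrected) and 11,977 (log odds). A one-sided test gives 8,984. None is within 3% of 9,690.

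Solving the pooled formula back from the three preintervention counts (8,019, 9,461, 9,857) gives risk ratios of 0.780, 0.797 and 0.801.

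**Step 2: where 0.78 comes from.** It is a weighted average of log odds ratios: 0.56^0.43 = 0.78. Collapsing the plan's risks directly instead: 0.43·p1 + 0.57·p0 = 0.098 with OR 1.8 gives p0 = 0.0754 and p1 = 0.1280. Full prevention moves everyone to 0.0754, which is OR 0.750 or risk ratio 0.769. The need is then 7,250 + 1,510 = 8,760.

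**Step 3: power under each meaning.**

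| Meaning of the effect | Power at 8,019 + 1,671 | Power at 8,019 + 2,005 |
|---|---|---|
| OR 0.78 | 73% | 79% |
| Risk ratio 0.78 | 80% | 86% |
| Collapsed risks, full prevention | 84% | 89% |

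**Step 4: the margin sentence against Table 3.**

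| | Planned | 80% row | 70% row |
|---|---|---|---|
| Intervention | 2,005 | 1,971 (34 fewer) | 2,054 (49 more) |
| Preintervention | 8,019 | 9,461 (1,442 more) | 9,857 (1,838 more) |
| Total | 10,024 | 11,432 (14% more) | 11,910 (19% more) |

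The 1,971 suffices only alongside 9,461 preintervention procedures. At 8,019 + 2,005, the effects implied by the two rows have 79.4% and 77.7% power. The 20% margin is 2,005 − 1,671 = 334 procedures, or 334/9,690 = 3.4% of the base total.

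**Step 5: treated percentage varied alone.** Using the collapsed risks, with no benefit from shorter hypotension, p_B = 0.098 − 0.43 × (fraction treated) × (0.1280 − 0.0754):

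| Treated | Overall OR | Power at 8,019 + 2,005 |
|---|---|---|
| 90% | 0.775 | 81% |
| 80% | 0.799 | 71% |
| 70% | 0.824 | 58% |

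Power reaches 80% at about 89% treated.

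**Step 6: the missing share.** If the rows use the same log-scale averaging, with short episodes also multiplied by the treated fraction, the risk-ratio reading implies 1-10 minute shares of about 0.33 and 0.35. The odds-ratio reading implies about 0.61 and 0.52, and 0.61 exceeds the 57% left after the 43%. These shares are inferred; the document does not state them.

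**The case against.** The best defence is that little turns on the scale. The planned size gives 79.3% power at OR 0.78, 80.6% at the less rounded 1.8^−0.43 = 0.777, and more under the other full-prevention readings. The risk-ratio reading is inferred from fit, since the plan names only the software. The unrounded 1.84 (OR 0.769) needs 9,375 unpooled and 10,367 pooled, which brackets the printed 9,690. All of this stands. It shows that the size is defensible, but not which effect it was computed for. The text says 1.8, 0.56 and 0.78 were used, and neither of those two totals equals 9,690.

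On the margin, the 20% was put on the intervention phase, where the 80% row fits and the 70% row is only 49 short. The preintervention figure is a calculated need from a retrospective cohort, not a recruitment cap. If the 275 procedures per month already count only patients with MAP below 65 mmHg, 36 and 7.5 months supply 9,900 and 2,062, enough for both rows. If the 60% has still to be applied, supply is 5,940 and 1,485 (36 and 9 months), enough for neither. The text does not settle this, so supply cannot rescue the sentence.

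The plan openly explains why it pairs lower treatment with benefit from short hypotension, and the treatment-only figures of 71% and 58% assume no such benefit. They are pessimistic bounds, not forecasts. They remain the direct test of the quantity that the sentence names.

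**Conclusion.** The point holds. Table 3's base row does not follow from an odds ratio of 0.78; it matches a risk ratio of 0.78 to within 0.2%. Read as the text states, the requirement is 18% higher and uses up the 20% margin (79% power at the planned size). The claim that the sensitivity analysis shows an error margin is contradicted by the table: both rows exceed the planned total and preintervention sizes, the 70% row also exceeds the intervention size, and neither reaches 80% power at the planned numbers.

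The shortfall in those rows is small, about 0.6 and 2.3 percentage points of power on the table's own scale. The study is not shown to be undersized under full prevention, since collapsing the plan's risks favours it (89%). Confidence is high on the margin sentence and on the mismatch with OR 0.78. That a risk ratio was actually used is the best fit, not proven.

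Every figure is for a simple comparison of two proportions with no clustering. The planned analysis is different ("As the study is an interrupted time series design, segmented regression models will be used for both primary end points"), and none of these powers applies to it directly.

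**What to change.** In the Sample size calculation and Table 3:

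- Declare one effect scale. Derive the overall effect once by collapsing the stated risks, and recompute every row from it.
- State the share of patients with MAP below 60 mmHg for 1-10 minutes, and the formula used.
- Report the power of 8,019 + 2,005 in every row, and add rows that vary only the treated percentage.
- Delete the margin sentence, or reword it to say that the sensitivity rows need more than the planned total.
- Note that these are two-proportion figures and not the power of the segmented regression.

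No increase in sample size is proposed. The cost is recalculation and wording. The full-prevention row will look better than it does now, and the reduced-treatment rows will look worse than the current text suggests.

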## Methods

### Design and participants

#### *Domain*

Adult elderly patients scheduled for a non-cardiac surgical procedure with a moderate to high surgical risk that have a low blood pressure (IOH) during the procedure.

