### Study population

All adult inpatients, 60 years and older, scheduled for a non-cardiac surgical procedure under general or central neuraxial anesthesia at the Vanderbilt University Medical Center (VUMC).

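### The feasibility sentence sets targets counted in procedures with MAP below 65 mmHg against 275 eligible procedures per month; as worded this gives 165 per month and a 26% shortfall, and the plan does not say whether 275 is already restricted

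*Combined protocol and SAP*

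**What the plan says.** All figures are in Sample size calculation unless another section is named.

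- Share with low pressure: "the incidence of any MAP below 65 mmHg were estimated at 60% for patients that meet the inclusion criteria".
- The AKI rate of 9.8% and the overall odds ratio of 0.78 are given for that subset. The 43% used to derive the odds ratio is too: "Within the study population (any MAP < 65 mmHg), the incidence of MAP < 60 mmHg for 10 minutes was 43" per cent.
- Targets: 8,019 preintervention and 2,005 intervention procedures. The Table 3 row "sample size without 20% error margin" gives 1,671 for the intervention phase.
- Feasibility: "With an average of 275 procedures per month meeting the inclusion criteria, the calculated sample size is feasible within the specified time periods".
- Statistical analysis, Primary end points: the analysis will "only include patients that have had a MAP below 65 mmHg for at least one minute during the procedure".
- Study population: "All adult inpatients, 60 years and older, scheduled for a non-cardiac surgical procedure under general or central neuraxial anesthesia". Neither this section nor Exclusion criteria contains a MAP condition.
- Domain, by contrast, describes patients "that have a low blood pressure (IOH) during the procedure".

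No section says whether the 275 was counted before or after the MAP restriction.

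**The concern.** A target counted in one population can be checked only against a monthly flow counted in the same population. The targets are for procedures with MAP below 65 mmHg. The 275 is described in almost the same words as the denominator of the 60%, which is the wider eligible group. On that reading the sentence leaves out the 60%.

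This sentence is the plan's only link between its targets and its calendar. If the 275 is the wider group, the stated size is not reached in the stated periods and the stated 80% power does not hold, so a null AKI result would be harder to interpret. Study design speaks of continuing until the estimated sample size is reached. However, it fixes the historic cohort at 36 months and the intervention period at 9 months, and it gives no extension rule.

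**Working it through.** **Inputs.** All are from Sample size calculation: 275 procedures per month; 60% with MAP below 65 mmHg; phases of 36 and 9 months; 7.5 effective intervention months, because half of the three-month trial period is dropped (7.5/43.5 = 0.17); AKI 9.8%; OR 0.78; power 0.80; alpha 0.05. Statistical analysis makes alpha two-sided.

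**1. Reproducing the plan's sample size.** The plan names no formula. Two versions come close to its figures.

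- Log odds ratio: N = (1.960 + 0.842)² / [f(1−f) · p(1−p) · (ln OR)²], with f = 7.5/43.5, p = 0.098 and OR = 1.8^(−0.43) = 0.777. This is 7.849 / (0.1427 × 0.0884 × 0.0639) = 9,741 in total (8,062 and 1,680). The plan has 9,690 (8,019 and 1,671).
- Two proportions, with pooled variance under the null: n₁ = [1.960·√(p̄(1−p̄)(1+1/k)) + 0.842·√(p₁(1−p₁) + p₂(1−p₂)/k)]² / (p₁−p₂)², with k = 7.5/36, p₁ = 0.098 and 0.78 applied as a risk ratio, so p₂ = 0.0764. This gives 8,010 and 1,669; 1,669 × 1.2 = 2,003, against the plan's 2,005.

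The second formula with 0.78 applied as an odds ratio gives 9,486 and 1,976. It does not reproduce the plan and is not used for the power figures below.

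**2. Monthly flow needed.** 8,019/36 = 222.75 procedures per month with MAP below 65 mmHg. (2,005/9 and 1,671/7.5 give about the same figure by construction, so this is a single check.) At 60%, 222.75/0.60 = 371 eligible procedures per month.

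**3. Yield under each reading of the 275.**

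| | 275 is all eligible | 275 is already MAP below 65 mmHg |
|---|---|---|
| Analysable per month | 275 × 0.60 = 165 | 275 |
| 36 months (target 8,019) | 5,940 | 9,900 |
| 9 months (target 2,005) | 1,485 | 2,475 |
| Against target | 1 − 5,940/8,019 = 26% short; 1 − 1,485/2,005 = 26% short | both met |

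Under the first reading, 1,485 is also below 1,671.

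**4. Power under the first reading.** Log odds ratio version: power = Φ(√[n₁n₂/(n₁+n₂) · p(1−p)] · |ln OR| − 1.96). For 5,940 and 165 × 7.5 = 1,237.5: 5,940 × 1,237.5 / 7,177.5 = 1,024.1; × 0.0884 = 90.5; square root 9.51; × 0.2527 = 2.40; minus 1.96 = 0.44; Φ = 67%.

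| Preintervention / intervention | Log odds ratio | Two proportions |
|---|---|---|
| 8,019 / 1,671 (plan, 7.5 months) | 80% | 80% |
| 5,940 / 1,237.5 (7.5 months) | 67% | 67% |
| 8,019 / 2,005 (plan, 9 months) | 85% | 86% |
| 5,940 / 1,485 (9 months) | 74% | 74% |

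The plan's 80% belongs to 1,671, that is, to 7.5 effective months. The matched comparison is therefore 80% with 67%. None of these figures allows for the time-trend terms of the planned segmented regression.

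**5. A clue to the second reading.** The most demanding Table 3 row, "70% of hypotension treated OR 1.2 MAP < 60 for 1-10 min", needs 9,857 and 2,054 procedures: 9,857/36 = 273.8 and 2,054/7.5 = 273.9 per month, just under 275. At 60% that would be 273.8/0.60 = 456 eligible procedures per month.

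**The case against.** The strongest case on the other side is that the 275 is already restricted to MAP below 65 mmHg and only its label is loose. Domain includes low blood pressure, and Patients at risk of IOH uses a MAP below 65 mmHg to identify patients at risk. Sample size calculation applies the term study population to the restricted subset before it reaches the 275. A restricted 275 covers every row of Table 3. It covers even the most demanding row with a 20% margin added (2,054 × 1.2 = 2,465 against 2,475; 9,857 against 9,900). The near match of 274 and 275 suggests that the authors set the 275 directly against these targets.

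This stands as a live possibility but does not settle the matter. The same near match would arise if the 60% had been left out by mistake. The 60% sentence makes sense only if the inclusion criteria carry no MAP condition, so the literal reading of the 275 remains the plain one.

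Two smaller points also stand. The 60% is stated for patients and the 275 for procedures, so applying one to the other is an assumption. The plan also has no section headed inclusion criteria.

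A reader might infer that the trial is shown to be underpowered, or that the 60% was overlooked. The documents support neither, because nothing in them identifies the population behind the 275. A reader might also quote a lower power, 66% at 9 months or 59% at 7.5 months, from the two-proportion formula with 0.78 as an odds ratio. That formula gives only 73% at the plan's own 8,019 and 1,671, so its result cannot fairly be set against 80%.

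**Conclusion.** The point holds as a conditional one. Either the sentence's conclusion is wrong, because 275 is the eligible flow and 165 per month are analysable, or its label is wrong, because 275 already counts procedures with MAP below 65 mmHg. The feasibility claim cannot be verified as it stands.

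In the first case both phases fall 26% short and power is about 67% instead of 80% on the plan's own basis. In the second case there is no shortfall.

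The first-case figures assume that the 60% applies to procedures as it does to patients, that the plan's 9.8% and treatment effect are right, and that there is no loss to trend terms. What is certain is the ambiguity, not the shortfall.

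**What to change.** Check in the perioperative data warehouse which population the 275 describes, then change the sentence in Sample size calculation.

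- **If it is all procedures eligible under Study population and Exclusion criteria:** state that 60% of 275, or 165 per month, are expected to have a MAP below 65 mmHg, giving 5,940 preintervention and 1,485 intervention procedures. Restate the power at about 67% (7.5 effective months), and remove the claim of feasibility within the specified periods.
- **If it is already restricted:** write *275 procedures per month with a MAP below 65 mmHg*, with 9,900 and 2,475 procedures expected.

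In both cases, use the term study population for one group only. The section of that name gives it to the unrestricted group, and Sample size calculation gives it to the restricted one.

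The cost is one data count and a wording change and, in the first case, a less favourable stated power. Keeping the targets in the first case would instead need 8,019/165 = 48.6 and 2,005/165 = 12.2 months. That would be a change of design and would have to be stated as one.
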